# **Venipuncture blood draw-** *Phlebotomy procedures will follow the World Health Organization's Guidelines on drawing blood: Best practices (6)*

- 1) **Overview**: Participant will be instructed not to eat or drink anything, other than water, after midnight the day of their baseline, 6-week, and 12-week visits. Phlebotomy of a peripheral arm vein will be performed by AUPCC clinicians (pharmacists and pharmacy residents) who have been phlebotomy trained, using sterile procedures and seated position. A sterile bandage will cover the phlebotomy site after the procedure and arm will be elevated to ensure that bleeding has stopped. The participant will be observed for any lightheadedness, bruising or bleeding during and after the procedure.
  - a) If the participant is lightheaded, he/she will be reclined until symptoms resolve

- b) If the participant is asymptomatic after the phlebotomy procedure, he/she will be released
- c) A maximum of 3 attempts to access a vein will be allowed at each visit, for each participant. If 3 unsuccessful attempts to access a vein are made, the participant will be excused from this portion of the study.

# 2) Materials

- a) Safety Needles, 22g or less; Butterfly needles, 21g or less
- b) Vacuum tube
- c) Tourniquets
- d) Antiseptic. Individually packaged 70% isopropyl alcohol wipes
- e) 2x2 gauze or cotton balls
- f) Sharps disposal container. An OSHA acceptable, puncture proof container marked "Biohazardous"
- g) Bandages or tape

# 3) Safety

- a) Observe universal (standard) safety precautions.
- b) Wash hands in warm, running water with approved handwashing product. Hands are to be washed before and after each phlebotomy is performed.
- c) Gloves are to be worn during all phlebotomies, and changed between patient collections. Palpation of phlebotomy site may be performed without gloves providing the skin is not broken.

# 4) **Procedure**

- a) Identify participant.
- b) Select the site (preferably at the bend of the elbow). Palpate the area; locate a vein of good size that is visible, straight, and clear. The vein should be visible without applying the tourniquet.
- c) Apply a tourniquet, 4-5 finger widths above the selected site.
- d) Ask the patient to forma fist so that the veins are more prominent
- e) Put on well-fitting, gloves.
- f) Disinfect the site using 70% isopropyl alcohol and allow to dry. DO NOT touch the site once disinfected.
- g) Anchor the vein by hold the patient's arm and placing a thumb BELOW the venipuncture site. **DO NOT touch the cleaned site; in particular, DO NOT place a finger over the vein to guide the needle.**
- h) Perform venipuncture. Enter the vein swiftly at a 30 degree angle.
- i) Once sufficient blood has been collected, release the tourniquet BEFORE withdrawing the needle
- j) Withdraw the needle gently and give the patient a clean gauze or dry cottonwool ball to press gently on the site. Ask the patient NOT to bend the arm.
- k) Discard the used needle and syringe or blood sampling device immediately into the sharps container
- 1) Check the label and forms on vacuum tube for accuracy

- m) Place items that can drip blood or body fluids into the "Biohazardous" waste container
- n) Remove gloves and place them in the general waste.
- o) Perform hand hygiene

**Urine collection** *A clean catch urine sample will be obtained from the participant. Procedures are derived from the U.S. National Library of Medicine. (7)* 

- 1) Participant will be instructed not to void immediately prior to baseline, 6-week, and 12- week appointments.
- 2) Participants will be given verbal and written instructions on how to provide a clean catch urine sample. Instructions will include:
  - a) You will use a special kit to collect the urine, it will include a cup and two wipes.
  - b) Wash your hand with soap and warm water
  - c) Females
    - i) Sit on the toilet with legs spread apart. Use two fingers to spread open the labia.
    - ii) Use a wipe to clean the inner folds of the labia. Wipe front to back.
    - iii) Use a second wipe to clean over the opening where urine comes out (urethra), just above the opening of the vagina.
    - iv) Keeping your labia open, urinate a small amount into the toilet bowl, then stop the flow of urine
    - v) Hold the urine cup a few inches from the urethra and urinate until the cup is about half full.
    - vi) You may finish urinating in the toilet bowl.
  - d) Males
    - i) Clean the head of the penis with a sterile wipe. If you are not circumcised, you will need to pull back (retract) the foreskin first.
    - ii) Urinate a small amount into the toilet bowl, and then stop the flow of urine.
    - iii) Then collect a sample of urine into the clean or sterile cup, until it is half full.
    - iv) You may finish urinating in the toilet bowl.

#### 4.4. Data collection instruments

 Clinical Data Recording Form (height measurement (inches), change in baseline body weight (%), change in total body weight (kg), Calculated BMI (kg/m2) measurement of body composition (using bioelectrical impedance analysis) (% body fat, pounds of fat, pounds of lean mass, pounds of total body water), waist measurement (inches), hip measurement (inches), Waist to Hip Ratio, Systolic blood pressure (mmHg), Diastolic blood pressure (mmHg), resting pulse (bpm), fasting blood glucose (mg/dL), fasting total cholesterol (mg/dL), fasting LDL-cholesterol (mg/dL), fasting HDL-cholesterol (mg/dL), fasting Triglycerides (mg/dL), total Cholesterol to HDL ratio, and ASCVD Score (%)), fasting insulin mI/L, fasting leptin ng/mL, IL-6 (pg/mL), tumor necrosis factor-α (pg/mL), urinary tyrosol and hydroxytyrosol.

- 2) International Physical Activity Questionnaire
- 3) Mediterranean Diet Nutrition Adherence and Knowledge Questionnaire
- 4) Diet History Questionnaire II (DHQ II)

#### 4.5. Data analysis

Descriptive statistics will be conducted and presented for the population. Baseline demographics will be compared between the 2 groups and compared using the appropriate test for each data point. Continuous variables will be compared using student t-tests, categorical variables will be compared using chi-square tests, etc. Age will be collected as a continuous variable (years). Ethnicity will be collected as a categorical variable (Caucasian, Asian, African-American, Hispanic, Other, Not Reported). Level of education will be collected as a categorical variable (high school, some college, college degree, graduate degree, professional degree, etc.), smoking status will be collected as a categorical variable (never smoked, past smoker, current smoker), baseline ASCVD risk score (collected as a continuous variable), obesity (dichotomous), HTN (dichotomous), hypercholesterolemia (dichotomous), Number of patients with 1 disease state (continuous), number of patients with 2 disease states (continuous), number of patients with 4 disease states (continuous), number of yellow values (continuous), number of red zone values (continuous).

Baseline data on change in baseline body weight (%), change in total body weight (kg), calculated BMI (kg/m2) measurement of body composition (using bioelectrical impedance analysis) (% body fat, pounds of fat, pounds of lean mass, pounds of total body water), waist measurement (inches), hip measurement (inches), Waist to Hip Ratio, Waist to Height Ratio, Systolic blood pressure (mmHg), Diastolic blood pressure (mmHg), resting pulse (bpm), fasting blood glucose (mg/dL), fasting total cholesterol (mg/dL), fasting LDL-cholesterol (mg/dL), fasting HDL-cholesterol (mg/dL), fasting Triglycerides (mg/dL), total Cholesterol to HDL ratio, and ASCVD Score (%)) fasting insulin mI/L, fasting leptin ng/mL, IL-6 (pg/mL), tumor necrosis factor-α (pg/mL), urinary tyrosol and hydroxytyrosol, will be compared to data at week-6 and the end of the 12 weeks

- Student's T test will be used to compare the continuous data collected in the study
- Chi Square test will be used to compare the categorical data collected in the study

The Diet History Questionnaire II, International Physical Activity Questionnaire, and the Mediterranean Knowledge/Adherence questionnaire will be collected at the beginning, mid-point and the end of the study. The number of drug-related problems identified through Medication therapy management will be collected at the beginning and end of the study

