# **1.2.** Brief description of methodology, including design, population, and variables of interest

This will be a prospective randomized controlled trial of Auburn University (AU) employees or an adult sponsored dependent of an active employee (<18 years old) who was insured by the AU Health and Pharmacy Insurance plan during 2015 and enrolled in the Health Insurance plan for 2016 and/or 2017. Eligible patients are 1) those completing their "Healthy Tigers" biometric screening between 01/01/2015-5/31/16, 2) who had a BMI  $\geq$  30 and two or more of the following CVD risk factors: male, age 55-80; female, age 60-80; current smoker; family history of premature coronary heart disease; received a red or yellow zone reading for their blood pressure, blood glucose, total cholesterol; those with a diagnosis of hypertension, pre-diabetes, or hypercholsterolemia; a patient of the AU Employee Pharmacy enrolled in the TigerMeds program with an existing diagnosis of hypertension, pre-diabetes, or hypercholesterolemia. Patients will be randomized into two groups: the AHA vs MD. The study will consist of a 12-week nutrition education program that includes dietary nutrition education sessions (both groups) and extra virgin olive oil and mixed nut supplementation (MD group). We will assess program impact by comparing baseline characteristics including body mass index, blood pressure, blood glucose, and total cholesterol, etc., and reassessing the same measures at week 6 and week 12 of the study.

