#### 2. Purpose

#### 2.1. Purpose of this project including research questions and/or aims

The primary objective of this pilot study is to assess the efficacy of a MD intervention (education + EVOO and mixed nut supplementation) versus that of an AHA nutrition intervention (education) on serum blood lipid levels as markers for cardiovascular disease risk. As secondary outcomes we will assess insulin resistance, serum metabolic factors, blood pressure, body mass index, and waist circumference.

Research Question: In the Southeastern United States, is the dietary pattern of the American Heart Association or a Mediterranean style diet more effective in the reduction of CVD risk factors.

Aim 1: To assess whether or not patients have improvements in their CVD risk factors by the end of the 12-week program.

Aim 2: To assess which dietary intervention is most effective in the reduction of CVD risk factors at the end of the 12-week program.

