# **Total Participant Involvement Time**

#### 340 minutes

- 5) STUDY REQUIREMENTS
  - a) The participants will be asked to follow a dietary pattern that is associated with their assigned intervention group. The Mediterranean Diet (MD) group will be given supplements of extra virgin olive oil (EVOO) and mixed nuts. Participants in this group will be asked use these supplements as a part of their daily intake. A total of 6 L of EVOO and 6 pounds of mixed nuts (3 pounds raw walnuts and 3 pounds raw almonds) will be administered throughout the study. Participants in the MD group will be given 3 L of EVOO and 3 pounds of mixed nuts at the baseline appointment asked to return unused portions of at their 6-week appointment. At that time they will be given a new supplementation of 3 L or EVOO and 3 pounds of mixed nuts. Participants will be given the same instructions for use and asked to return unused portions at the end of the study (week 12).
  - b) The participants might have follow-up appointments scheduled with the pharmacist within the AUPCC depending on the patient's personal care plan that is developed at baseline. For instance, if a patient has potential or actual drug-related problems that are identified on their baseline MTM appointment, then the pharmacist will schedule follow-up appointments that are appropriate for the problem and the plan of care that is developed to address these problems. This will be done consistently between all patients in the study, regardless of the randomization (the pharmacist and the will be blinded concerning which group the patient is randomized to concerning dietary intervention).
  - c) Narrated nutrition education presentations will be developed by a registered dietitians, dietetic interns, graduate students, and faculty. These presentations will be loaded on the "Healthy Hearts Program" website. The participants will be asked one presentation weekly for the first 6 weeks of the study and then one additional education module at week 9. A post-presentation assessments will load after the presentation is completed, and completion of the assessment will be used as verification that the participant watched the presentation.
  - d) The participant will complete the following at baseline, week-6 and week 12 of the study: Diet History Questionnaire II, International Physical Activity Questionnaire, and a Mediterranean diet knowledge and adherence questionnaire.

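### The analysis section states no Mediterranean-versus-AHA comparison for any outcome, so the primary objective and Aim 2 have no stated test

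*Combined protocol and SAP*

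**What the plan says.** Section 2.1 sets a comparative question: "The primary objective of this pilot study is to assess the efficacy of a MD intervention" against an AHA education intervention, on serum lipids. Aim 1 asks whether participants improve by week 12. Aim 2 is "To assess which dietary intervention is most effective in the reduction of CVD risk factors at the end of the 12-week program".

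Section 4.5 covers the analysis in three steps:

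- **Baseline.** "Baseline demographics will be compared between the 2 groups", using t-tests and chi-square tests. The groups are mentioned nowhere else in the section.
- **Outcomes.** After a list that includes all the lipids, the section says that the baseline data "will be compared to data at week-6 and the end of the 12 weeks". Arm is not mentioned.
- **Tests.** One bullet reads "Student's T test will be used to compare the continuous data collected in the study". A parallel bullet gives chi-square for categorical data. Neither says which groups or visits are compared, or whether the t-test is paired.

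The section ends with the collection times of the questionnaires and the drug-related problem count, and states no comparison for them. Section 1.2 describes impact in the same before-and-after way: "We will assess program impact by comparing baseline characteristics" and then measuring the same variables again at weeks 6 and 12.

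**The concern.** Change from baseline in either arm mixes the effect of the diet with whatever both arms share. Both arms receive nutrition education, and all participants receive a pharmacist's medication review. On the pharmacist follow-up, section 4.2 says: "This will be done consistently between all patients in the study, regardless of the randomization". Section 6.1 expects participants to improve without distinguishing the arms. Only the difference between randomised arms removes these shared effects.

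An analyst could therefore carry out the stated contrast in full and never test the primary objective. Running it separately in each arm and comparing the p-values does not repair this, because one arm can reach significance and the other not when the diets are equally effective.

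If the generic bullet is taken to mean a between-arm t-test, the question is answered. The choice between week-12 value and change then stays open until the data are seen, and the baseline measurement is not used as well as it could be.

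**Working it through.** **Text check.** Each question in section 2.1 is set against what section 4.5 states.

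| Question | Contrast needed | Stated in 4.5? |
|---|---|---|
| Primary objective: lipids, MD versus AHA | Between arms at follow-up | No |
| Aim 1: improvement by week 12 | Within participant | Yes, but not stated as paired |
| Aim 2: which diet is more effective at week 12 | Between arms at week 12 | No |

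The plan has no figure to reproduce: it gives no sample size, alpha, SD, correlation or effect. Everything below is illustrative. Assumptions: equal arms of n, outcome SD of 1 at each visit, correlation rho between baseline and week 12, and a two-sided 5% test.

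**1. The stated contrast when the diets do not differ.** Both arms improve by 0.4 SD. A paired test on all 2n participants has SE = sqrt(2(1 − rho)/(2n)). For n = 30 and rho = 0.7, SE = sqrt(0.6/60) = 0.10, so the noncentrality is 0.4/0.10 = 4.0 on 59 df.

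| n per arm | rho 0.3 | rho 0.5 | rho 0.7 |
|---|---|---|---|
| 20 | 55% | 69% | 89% |
| 30 | 73% | 86% | 98% |
| 50 | 92% | 98% | 99.9% |

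The entries are the chance of a significant pooled before-after test. A between-arm test is significant in 5% of such trials; a simulation of 20,000 trials at n = 30 and rho = 0.7 gave 5.0% for week-12 value, change and ANCOVA alike.

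**2. The stated contrast run separately by arm.** If each arm is significant with probability p, the chance that exactly one is significant is 2p(1 − p). For n = 30 and rho = 0.7, p = 0.78, which gives 2 × 0.78 × 0.22 = 34%. Over the nine cells above, the figure runs from 10% to 49%. None of these trials has a real difference between diets.

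**3. The between-arm reading.** The variance of the arm difference, relative to the week-12 value, is 1 for the value, 2(1 − rho) for change and 1 − rho² for ANCOVA (regression on arm and baseline).

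| rho | Value | Change | ANCOVA |
|---|---|---|---|
| 0.3 | 1.00 | 1.40 | 0.91 |
| 0.5 | 1.00 | 1.00 | 0.75 |
| 0.7 | 1.00 | 0.60 | 0.51 |
| 0.8 | 1.00 | 0.40 | 0.36 |

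For n = 30, the SE is sqrt((2/30) × factor), and the ANCOVA variance is inflated by 1 + 1/(2n − 4) for estimating the slope. At rho = 0.7 the 95% CI half-widths are 0.52, 0.40 and 0.37 SD. Power for a true 0.5 SD difference is:

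| rho | Value | Change | ANCOVA |
|---|---|---|---|
| 0.3 | 48% | 36% | 51% |
| 0.7 | 48% | 69% | 75% |

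Which unadjusted test is better depends on rho. ANCOVA has the lowest variance at each rho examined.

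**4. Aim 1 with an unpaired test.** The unpaired SE is too large by a factor of 1/sqrt(1 − rho): 1.20, 1.41 and 1.83 at rho 0.3, 0.5 and 0.7.

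**The case against.** The best defence is that a between-arm test is implied. The t-test and chi-square are first introduced in 4.5 for comparing the groups, and the closing bullets repeat them without limiting them to baseline. Ordinary chi-square assumes independent groups, which fits an arm comparison better than repeated measures on the same people. The outcome list includes weight-change variables, which have no baseline value of their own to be compared with. Aim 2 fixes week 12, and its reference to reduction points towards change. If change is meant, the gain from ANCOVA is modest at high correlation (75% against 69% power at rho 0.7), and section 2.1 calls the study a pilot.

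Part of this stands. The arm comparison is unstated, not excluded, and a two-sample t-test would be valid. The contrast in step 1 of the working follows from its set-up, and nothing in the plan says that a pooled before-after test would be used to rank the diets. The choice of primary lipid and the rule for missing values are also separate from the core defect.

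The rest does not stand. None of these pointers states an arm contrast for any outcome, and the sentence directly before the bullets is a before-after comparison. Aim 2 does not settle value against change, and at rho 0.3 a change score loses substantially to ANCOVA (36% against 51%). Pilot or not, the stated primary objective is comparative efficacy.

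**Conclusion.** The concern holds and should be fixed before analysis. As written, section 4.5 states an analysis for Aim 1 and none for the primary objective or Aim 2. This conclusion rests on the text alone and needs no assumed figure.

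The practical size depends on the reading. On the literal reading, the randomised question goes untested and shared improvement could be mistaken for evidence about the diets. On the generous reading, the question is answered, but the outcome form is open and precision is lost. At 30 per arm, ANCOVA gains 3 to 15 percentage points of power over the unadjusted tests at rho 0.3, and 6 to 27 points at rho 0.7. These sizes rest on assumed n, correlation, effect and equal variances.

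**What to change.** Replace the two test bullets in section 4.5 with the following.

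- **Primary analysis.** Name one lipid variable at week 12. Estimate the MD minus AHA difference with a 95% CI from a linear model on arm and the baseline value, with participants analysed in their assigned arm.
- **Alternative.** Use a mixed model of weeks 6 and 12 with arm, visit, arm-by-visit and baseline, and report the week-12 contrast. This is preferable if blood draws are missed, because a participant with only a week-6 value still contributes. Section 4.3 foresees missed draws: after three failed attempts, "the participant will be excused from this portion of the study".
- **Missing values.** Report the number without a week-12 lipid value in each arm. Add a sensitivity analysis for participants with no follow-up value, who enter neither model.
- **Secondary outcomes.** Use the same model for the continuous ones.
- **Aim 1.** Report paired baseline-to-week-12 changes with CIs as descriptive. Draw no conclusion about relative efficacy from within-arm p-values.

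The first bullet is the essential change; the others complete it. The cost is a rewrite of section 4.5, one decision on the primary lipid and one missing-data rule. No new data, visits or participants are needed.

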- c) All subjective and objective medical information collected during this appointment will be recorded in the CompuGroup Medical (CGM) electronic medical record (EMR) that is used in the Auburn University Pharmaceutical Care Center (AUPCC) and the "Healthy Tigers" programs. This EMR is a secure medical record that meets all HIPAA requirements and has been reviewed by the Harrison School of Pharmacy (HSOP) HIPAA officer, the Auburn University HIPAA officer, and the AU HIPAA consultant, and meets all legal and security requirements. These data will be perpetually stored in this EMR as required of medical data. Access to this EMR is restricted to authorized personnel only.
- 3) Baseline, 6 week and 12 week Appointments
  - a) Participants will then return to the Auburn University Pharmaceutical Care Clinic (AUPCC) for their baseline "Healthy Tigers" Healthy Hearts Program visit. Pharmacists and pharmacy residents, employed by the AUPCC will obtain the following: height measurement (inches), weight measurement (pounds), Calculated BMI (kg/m2) measurement of body composition (using bioelectrical impedance analysis) (% body fat, pounds of fat, pounds of lean mass, pounds of total body water), waist measurement (inches), hip measurement (inches), Waist to Hip Ratio, Waist to Height Ratio, Systolic blood pressure (mmHg), Diastolic blood pressure (mmHg), resting pulse (bpm), fasting blood glucose (mg/dL), fasting total cholesterol (mg/dL), fasting LDL-cholesterol (mg/dL), fasting HDL-cholesterol (mg/dL), fasting Triglycerides (mg/dL), total Cholesterol to HDL ratio, Atherosclerotic cardiovascular disease risk (ASCVD) Score (%), fasting insulin mI/L, fasting leptin ng/mL, IL-6 (pg/mL), tumor necrosis factor-α (pg/mL), plasma α linolenic acid, urinary tyrosol and hydroxytyrosol. These measurements will be repeated at week 6 and week 12 of the trial.

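### Section 4.5 states no between-arm analysis of the outcomes and no baseline adjustment, although the lipid objective and Aim 2 are between-arm questions; an ANCOVA on baseline values already collected would supply both.

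*Combined protocol and SAP*

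**What the plan says.** The whole analysis plan is section 4.5. For continuous data it states that "Student's T test will be used to compare the continuous data collected in the study", without saying whether the test is paired or unpaired, or whether week-12 values or changes are analysed. The sentence on outcomes opens with "Baseline data on change in baseline body weight (%), change in total body weight (kg", lists the remaining measures, and says that these data "will be compared to data at week-6 and the end of the 12 weeks". That is a comparison over time. The only comparison in 4.5 that is explicitly between arms concerns patient characteristics at entry: "Baseline demographics will be compared between the 2 groups and compared using the appropriate test for each data point". No ANCOVA, regression, mixed model or other baseline-adjusted method appears anywhere in the document.

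The questions, however, are between-arm. Section 1.2 sets the design: "Patients will be randomized into two groups: the AHA vs MD". Section 2.1 makes the primary objective the efficacy of one intervention versus the other "on serum blood lipid levels as markers for cardiovascular disease risk". Aim 2 is "To assess which dietary intervention is most effective in the reduction of CVD risk factors at the end of the 12-week program".

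The covariate is already in hand. Section 4.2 lists the lipids and the other clinical measures at the baseline visit and adds: "These measurements will be repeated at week 6 and week 12 of the trial".

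**The concern.** The stated analysis does not match the stated question. Section 4.5 can be read in three ways:

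1. Tests within person, baseline against week 6 and week 12. This is the most literal reading. It serves Aim 1 but leaves the primary objective and Aim 2 without a test.
2. An unpaired t-test of week-12 values between arms. This is valid, but it ignores the baseline value.
3. An unpaired t-test of change from baseline between arms. This is also valid, and the change variables listed for body weight point this way. But it subtracts the whole baseline value whatever the correlation.

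Under the first reading, a reader of the results may be left with one p-value per arm and conclude that the diets differ because one is significant and the other is not. That inference does not control error. Under the second and third, the trial gives up precision that it has already paid for, and the plan does not say which of the two applies. The better choice depends on a correlation that the documents do not give.

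**Working it through.** **Inputs.** The documents give no sample size (section 3.2 recruits until the project is full, with no number), no alpha, SD, effect size or allocation ratio, and no correlation between baseline and week 12. There is therefore no figure of the plan's own to reproduce. Assumed: 1:1 allocation, two-sided 0.05, normal data, equal SD σ at both visits, true difference 0.5 SD, 10 to 50 per arm, and correlation ρ mainly 0.3 to 0.7, with 0 and 0.9 as limits.

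**Separate within-arm tests.** Suppose the diets work equally well and each within-arm test has 50% power. The chance that exactly one arm reaches significance is 2 × 0.5 × 0.5 = 50%. Section 6.1 expects benefit in both arms, so this case is not far-fetched.

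**Variance of the arm difference, n per arm.**
- Week-12 t-test: 2σ²/n
- Change t-test: (2σ²/n) × 2(1 − ρ)
- ANCOVA, large sample: (2σ²/n) × (1 − ρ²)

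ANCOVA is therefore 1 − ρ² of the week-12 test and (1 − ρ²)/[2(1 − ρ)] = (1 + ρ)/2 of the change test:

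| ρ | against week-12 t | against change t |
|---|---|---|
| 0.3 | 1 − 0.09 = 0.91 | 1.3/2 = 0.65 |
| 0.5 | 1 − 0.25 = 0.75 | 1.5/2 = 0.75 |
| 0.7 | 1 − 0.49 = 0.51 | 1.7/2 = 0.85 |

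**Price of the estimated slope.** The ANCOVA variance is inflated by about 1 + 1/(N − 4), with N the total: 1.06 at N = 20 and 1.02 at N = 60. Setting (1 − ρ²)(N − 3)/(N − 4) = 1 gives break-even with the week-12 test at ρ = √[1/(N − 3)]: 0.24 at N = 20 and 0.13 at N = 60. Break-even with the change test is at ρ = 1 − 2/(N − 3), which is 0.88 at N = 20.

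**Power by simulation** (40,000 runs per setting, effect 0.5 SD):

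| per arm | ρ | week-12 t | change t | ANCOVA |
|---|---|---|---|---|
| 10 | 0 | 18.5% | 11.7% | 17.6% |
| 10 | 0.3 | 18.6% | 14.8% | 19.1% |
| 10 | 0.5 | 18.3% | 18.7% | 22.1% |
| 30 | 0 | 47.9% | 27.2% | 47.3% |
| 30 | 0.3 | 48.0% | 36.4% | 50.9% |
| 30 | 0.5 | 48.3% | 48.3% | 59.0% |
| 30 | 0.7 | 47.8% | 68.9% | 75.0% |
| 30 | 0.9 | 47.9% | 98.9% | 99.1% |

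With no true difference, all three methods rejected in about 5% of runs. At 20 and 50 per arm with ρ = 0.5, the t-tests reach about 34% and 70%, and ANCOVA about 42% and 81%.

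**Choosing the wrong t-test** at 30 per arm costs about 12 points at ρ = 0.3 (48.0 − 36.4, change chosen) and about 21 points at ρ = 0.7 (68.9 − 47.8, week 12 chosen). ANCOVA removes the need to choose.

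**The case against.** **The precision argument is a preference, not an error.** This stands. On either between-arm reading the t-test is valid, section 2.1 calls the study a pilot, and no power target is stated that could be missed. A reader might infer that the planned t-test inflates type I error or biases the diet comparison. The documents do not support that: both unpaired t-tests hold their level. The warning about error control applies only if a diet difference is inferred from separate within-arm results. Section 4.5 does not say that the investigators will do this; it only leaves the way open.

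**The gain is assumed, and may be small.** This also stands. Nothing in the documents fixes the sample size or the correlation. With about 10 per arm the gain over the better t-test is under 1 point at correlation 0.3 and about 4 points at 0.5. At correlation 0 ANCOVA loses about 1 point or less. At 0.9 it adds almost nothing to the change score. The power figures say nothing about a within-person reading, where the issue is a missing test. Nor do they show that the trial is underpowered, since its size is not given.

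**Adjustment can lose participants.** This is a fair point. Under section 4.3, three failed attempts at a vein excuse a participant from the blood draw at that visit. Someone without a baseline lipid but with a week-12 value would stay in a week-12 t-test and drop out of a complete-case ANCOVA. The fix has to deal with this.

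**It leaves another gap open.** ANCOVA does not decide which lipid is primary. That choice is missing too, and is a separate matter.

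**Conclusion.** The point holds as something to consider, with medium confidence. What the text establishes is that section 4.5 states neither a between-arm analysis of outcomes nor any baseline adjustment, while the primary objective and Aim 2 need the first and the collected data allow the second. If the literal within-person reading is meant, the missing test is the main defect and no power figure describes it. If an unpaired t-test is meant, the analysis is sound and the loss is one of precision: ANCOVA has 51 to 91% of the variance of the week-12 test and 65 to 85% of that of the change test, over correlations of 0.3 to 0.7. At 30 per arm and 0.5 SD, that is about 3, 11 and 6 points of power over the better t-test at 0.3, 0.5 and 0.7. These sizes rest wholly on assumed inputs. The recommendation depends on them less, because ANCOVA was at or above the better t-test at every correlation from 0.3 to 0.9 at 30 per arm and cost little at 0.

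**What to change.** State in section 4.5, before outcomes are seen by arm:

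- **Main between-arm analysis.** For each continuous outcome measured at baseline, including the lipids, fit an ANCOVA with the week-12 value as outcome, arm as factor and the baseline value of the same measure as covariate. Report the adjusted MD minus AHA difference with its 95% CI. For body weight, model week-12 weight on arm and baseline weight.
- **Week 6.** Use the same model, as secondary.
- **Within-arm changes.** Report them as descriptive, and do not use them to compare the diets.
- **Missing baseline values.** Keep such participants by a simple pre-specified rule, for example by setting the missing baseline covariate to the overall mean of both arms combined.
- **Optional sensitivity analysis.** Add a log-scale ANCOVA for markers expected to be right-skewed. It estimates a ratio of geometric means instead of a mean difference, and it can gain or lose power depending on the true distribution, so it should not replace the main analysis by default.

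The cost is wording, one degree of freedom per model and the missing-baseline rule. No visit, assay or participant is added, and the raw-scale model still estimates a difference in means.
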